3.2.1 Primary Outcome Measures

The barostat device will measure the volume changes in the rectum during controlled distension of the gastrointestinal organs. If the TEA is successful, the study participant's maximum tolerance should increase after TEA compared to their first maximum tolerance of the visit. This will be defined by comparing their maximum tolerance pre and post TEA.

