4.1 Schedule of Events for Each Visit

Every visit is the same and will follow the steps detailed below, with the exception of the first visit which will include the informed consent process. At visit one, the study team will randomly generate the stimulations schedule unique to each study participant; this is the order of locations and currents by using a random generator. For example, ST36-100Hz, ST36-25Hz, PC6-100Hz, PC6-25Hz and Sham-TEA.

48 Hours prior to the visit: The study participants will not take any medications known to affect the gut or pain perception.

8:00 pm on the night before the visit: The study participants begin fasting for their visit the next day. Study participants can still drink water. Study participants cannot drink coffee, tea, juices or eat any food items.

Day of the Visit:

Study participants will come to the study location, the Gastrointestinal Physiology Lab in University of Michigan. The visit will take place in one of the private rooms within the lab. **If the study participant is a women of child bearing potential:** She will complete a pregnancy test provided by the study team. If her pregnancy test is positive, she will be excluded from further participation in the study and will not complete the visit.

Rome IV Criteria for Irritable Bowel Syndrome: Upon arrival for every visit, the study participant will complete the Rome IV Criteria for Irritable Bowel Syndrome survey.

Enema: The study participant will be given a rectal enema to clean the rectum. Then the study participant will undress from the bottom down and be given a gown and sheets for comfort and privacy.

Position the study participant: The study participant will be asked to lie down on the medical examination table on one side and bring his or her knees up to the chest, similar to the fetal position. The table has rails that will protect the study participant from falling. The staff may use pillows to adjust and secure the study participant as well as for comfort.

Electrode Placement: The GI physiology laboratory staff will place two electrocardiogram (ECG) electrodes from of the TEA device on the subject's skin, one on the wrists at location PC6 and the other

Fig.1: Locations of PC6 and ST36.

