5.1 Study participant Inclusion Criteria

In order to be eligible to participate in this study, a study participant must meet all of the following criteria:

- Male or female, aged 18 to 99
- Willing to comply with all study procedures and be available for the duration of the study
- Diagnosed with IBS-C satisfying Rome IV criteria
- Have symptoms present for at least the last 3 months
- Have abdominal pain that is not adequately relieved at the time of screening and the time of randomization
- Has a VAS pain score of >3 (on 0-10 score)

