5.4 Treatment Assignment Procedures

5.4.1 Randomization Procedures

Prior to the first visit, the order of TEA stimulation at the visits will be randomly assigned to each study participant. Every study participant will undergo every TEA combination (For example, ST36-100Hz, ST36-25Hz, PC6-100Hz, PC6-25Hz and Sham-TEA).

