7.1 Screening

Once a candidate is identified, a member of the study team will speak with the study participant to explain the study. The study participant may be contacted via phone and the study team member will follow the phone script and go through the pre-screen questions if interested. If the study participant is determined to be ineligible or not interested via the pre-screening contact, he or she will be excluded in the study and logged as pre-screened and ineligible or not interested.

If the study participant is eligible and interested the study team will set up the first study visit. The study participant will go through the informed consent process at the first study visit.

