9.4 Safety Oversight

Data and Safety Monitoring Board (DSMB)

The first DSMB meeting will occur one month after recruitment begins. In addition to reviewing Serious Adverse Events (SAEs), the first DSMB meeting will focus on over all safety of the trial and study agent and will make a determination as to whether or not the study should proceed. The DSMB will then meet once every 6 months throughout the remainder of the study and at any time during the study in which an unexpected and possibly related SAE occurs.

The DSMB will be composed of the following members:

[name]: a Gastroenterologist and Professor of Medicine from the Division of Gastroenterology, Texas Tech University Health Science Center. [name] is an established clinical investigator in the field of functional gastrointestinal diseases. She will serve as the Chair of the committee.

[name]: a Gastroenterologist and [name]., Chair in Gastroenterology Gastrointestinal Motility Clinic from the Division of Gastroenterology at the University of Louisville. [name] is an expert in functional gastrointestinal diseases and has extensive experience in clinical trials and clinical research. He will serve as a member of the committee.

[name], PhD: an Assistant Professor of Medicine and Director of Gastrointestinal Motility, Division of Gastroenterology and Hepatology MetroHealth Medical Center, Case Western Reserve University, Cleveland, Ohio. He will serve as a member of the committee

[name]: a lead statistician from University of Michigan, Michigan Institute for Clinical & Health Research. He has over 15 years of experience on translational and health research projects across various disease area. He will serve as a member of the committee.

10 Statistical Considerations

Analysis of variance (ANOVA) will be performed to investigate the difference in each of the outcomes among 4 different sessions. Tukey's test will be used for study the differences in each of the measurements between two stimulation points (same stimulation parameters) and between two stimulation parameter sets (same stimulation points). The Pearson correlation analysis will also be performed to investigate the correlation between each of HRV parameters and the pain score or sensation threshold

. 10.1 Study Hypotheses

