10.2 Sample Size Considerations

The study team plans for a 20% participant dropout or incompletion rate. For this reason, they will enroll 25 study participants when in actuality they need 20 study participants to complete the study. If 20 study participants complete the study and there are still 5 active participants, the active participants will still complete the study.

This is **not** a clinical trial to investigate the efficacy of the therapy for the treatment of IBS-C. Instead, this is a pilot study to determine which method of TEA (4 different modalities and 1 placebo) is more effective in treating abdominal pain in patients with IBS-C by studying patients' sensation to rectal distention with different methods of treatment. The findings of this pilot study will be used to determine which treatment to use in a future clinical trial. No preliminary data are available for the calculation of the sample size. The sample size stated in this study was based the PI's experience in other neuromodulation studies involving methodological optimization.

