10.3 Final Analysis Plan

Analysis of variance (ANOVA) will be performed to investigate the difference in each of the outcomes among different sessions. Tukey's test will be used for study the differences in each of the measurements between two stimulation points (same stimulation parameters) and between two stimulation parameter sets (same stimulation points). The Pearson correlation analysis will also be performed to investigate the correlation between each of autonomic function parameters and the pain score or sensation threshold.

11 Source Documents and Access to Source Data/Documents

Only members of the study team will have access to source data. This includes: all information, original records of clinical findings, observations, or other activities in a clinical trial necessary for the reconstruction and evaluation of the trial.

12 Quality Control and Quality Assurance

- The study team will be present for each visit and follow the visit CRFs. The study team will go through the procedures with the GI physiology lab staff members to ensure that there is adherence to the protocol.
- The study team will sign the bottom of each study CRF at the end of the visit.

13 Ethics/Protection of Human Study participants

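### The ANOVA names no participant or visit term and the visit orders are not balanced: estimates stay unbiased, but power may be lost, and precision too if the change trends over visits

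*Combined protocol and SAP*

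**What the plan says.** Every participant receives four TEA modalities and sham, one per visit, over five visits.

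- **Order.** Section 4.1 has the team, at visit one, "randomly generate the stimulations schedule unique to each study participant; this is the order of locations and currents by using a random generator". Section 5.4.1 says: "Prior to the first visit, the order of TEA stimulation at the visits will be randomly assigned to each study participant". Neither gives a block, Latin square or other balancing rule. If 'unique' means that no two orders repeat, that still does not balance conditions over visits.
- **Analysis.** Section 10 opens with: "Analysis of variance (ANOVA) will be performed to investigate the difference in each of the outcomes among 4 different sessions". Section 10.3 repeats this without the count: "Analysis of variance (ANOVA) will be performed to investigate the difference in each of the outcomes among different sessions". Tukey's test and Pearson correlation follow. No participant, visit or repeated-measures term is named, and no error term is given for Tukey's test.
- **Primary outcome.** Section 3.2.1 compares maximum tolerance within the visit: "This will be defined by comparing their maximum tolerance pre and post TEA".
- **Use of the result.** Section 10.2: "The findings of this pilot study will be used to determine which treatment to use in a future clinical trial".

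**The concern.** The pilot's product is a ranking of modalities from 20 to 25 people, so the precision of within-participant comparisons is what it has to offer. Two features of the plan could waste some of it.

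The first does not depend on anything happening over visits. If sessions are compared as though they were independent groups, differences between participants go into the error term, although the design removes them from the condition means.

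The second is conditional. With an independent random order for each participant, conditions fall unevenly over visits by chance. A shift common to both inflations of a visit cancels in the pre/post change. A trend in the change itself, such as habituation to repeated distension, would not cancel, and without a visit term it becomes noise in every comparison.

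**Working it through.** **The plan's own figure.** Section 10.2 needs 20 completers and allows 20% loss: 20 / (1 − 0.20) = 25, as stated. There is no power calculation, and the documents give no SD, correlation, effect size or visit trend.

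**Assumptions made here.** Residual within-participant SD of the change = 1; one condition better by 0.4 SD; two-sided 5% level; within-participant correlation ρ of the change = 0, 0.3, 0.5; linear visit trend d = 0, 0.1, 0.2, 0.4 SD per visit (0, 0.4, 0.8, 1.6 SD from visit 1 to visit 5); no carryover.

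**(a) Participant term, no trend.** With complete data, participant differences cancel in the condition means, so the ranking does not change. The one-way error mean square has expectation 1/(1 − ρ) instead of 1. The error SD is therefore √(1/0.7) = 1.20 at ρ = 0.3 and √(1/0.5) = 1.41 at ρ = 0.5. Simulated ANOVA at N=25:

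| ρ | One-way: type I error | One-way: power | Participant fitted: type I error | Participant fitted: power |
|---|---|---|---|---|
| 0 | 5.0% | 25.0% | about 5% | about 25% |
| 0.3 | 1.1% | 9.6% | about 5% | about 25% |
| 0.5 | 0.2% | 2.8% | about 5% | about 25% |

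The one-way test is conservative; its error rate is not inflated.

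**(b) Visit trend, unrestricted orders, no visit term.** Within a participant, the visit positions of two conditions each have variance 2 and covariance −0.5. Their difference has variance 2 + 2 + 1 = 5. The variance of a condition difference is then (2 + 5d²)/N = (2/N)(1 + 2.5d²).

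The pilot chooses among four TEA modalities, with sham as comparator. With k = 0.4√N / √(1 + 2.5d²), the chance that the truly best modality ranks first is ∫ φ(z − k) Φ(z)³ dz:

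| d | Variance increase | N=25: k | N=25: chance | N=20: k | N=20: chance |
|---|---|---|---|---|---|
| 0 | 0% | 2.00 | 82.3% | 1.79 | 77.6% |
| 0.1 | 2.5% | 1.98 | 81.8% | 1.77 | 77.1% |
| 0.2 | 10% | 1.91 | 80.3% | 1.71 | 75.6% |
| 0.4 | 40% | 1.69 | 75.2% | 1.51 | 70.5% |

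A balanced list with visit fitted has contrast variance 2/N at any linear d, so it stays near the d = 0 row.

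**(c) What each remedy contributes.** Fitting visit on unrestricted orders costs on average 4.4% in contrast variance at N=25 and 5.6% at N=20. It breaks even at d = √(0.044/2.5) = 0.13 and √(0.056/2.5) = 0.15. A balanced list removes that cost.

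Balancing without fitting visit is worse than either. At N=25 with participant fitted, type I error falls to 4.9, 4.4, 3.3, 1.1% and power to 24.9, 23.6, 19.9, 9.7% over the four values of d. With visit fitted on the balanced list, power is 24.7 to 25.0%.

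If 5 of 25 participants drop out at random from a balanced list, contrast variance is 1.011 times that of a balanced 20. Partly completed sequences were not modelled.

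**The case against.** The ANOVA is unspecified, which is not the same as wrong. In a study where everyone receives every condition, repeated measures is a natural reading, and the power loss in (a) describes only the literal one. That stands: the request is to state the model, and no demonstrated error is claimed.

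The visit argument rests on a trend that no document reports. The loss of about 7 points needs a drift of 1.6 SD in the change across five visits; at d = 0.1 the loss is about half a point. At d = 0 the balanced list gains nothing over the plan with participant fitted. That stands too.

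A reader might infer that unrestricted random orders bias the comparison, or that the ranking is unreliable as planned. The documents do not support either. Independent random orders are valid, any imbalance is chance, and the outcome is measured within the visit.

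A reader might also take the conflict over when orders are generated as a threat to the results. Section 4.1 places it at visit one and Section 5.4.1 before it, while Section 7.1 says: "The study participant will go through the informed consent process at the first study visit". Section 5.1 has a criterion judged at randomization: "Have abdominal pain that is not adequately relieved at the time of screening and the time of randomization". The conflict is real, and under Section 5.4.1 the order would precede consent. But every participant is due all five conditions, so knowing the order leaves much less room for selection than knowing an arm would. No effect on results is claimed.

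Finally, this is a pilot that disclaims efficacy assessment. Even so, Section 10.3 plans formal tests, and those need a stated error term.

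**Conclusion.** The point holds as a low-cost improvement, worth considering; it is not a flaw that invalidates the pilot. The part that needs no trend is the stronger one: a literal one-way ANOVA would cut power at N=25 from about 25% to 9.6% or 2.8% at assumed correlations of 0.3 or 0.5. The visit part is conditional: at d = 0.4 it costs about 7 points in the chance of choosing the best modality (82.3 to 75.2% at N=25; 77.6 to 70.5% at N=20), and with no trend it costs nothing. Naming the model does most of the work. The list adds about 4 to 6% of contrast variance, and only relative to fitting visit on unrestricted orders. All sizes rest on the assumed SD, correlation, effect and linear trend.

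**What to change.** 1. In Sections 10 and 10.3, state the model as participant, condition and visit, and use its residual for Tukey's test. Make the session count in Section 10 agree with the five-session design.
2. In Sections 4.1 and 5.4.1, draw orders from a concealed, pre-generated list in blocks of five that balances conditions over visits. Any 5×5 Latin square does this. Do not balance the orders without fitting visit.
3. If orders stay unrestricted, still fit participant, and treat the visit term as insurance against a trend.
4. As a wording point, reconcile Sections 4.1 and 5.4.1 on timing. For instance, prepare the list in advance and release each participant's order only after consent and eligibility are confirmed at visit 1.

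**Cost.** A sentence on the model, a paragraph on the list, and the list itself. Visit uses 4 of 96 error degrees of freedom at N=25: 125 − 1 − 24 − 4 = 96. At N=20 it uses 4 of 76: 100 − 1 − 19 − 4 = 76. The list must stay concealed so that the last order in a block cannot be predicted. Dropout and incomplete sequences will partly undo the balance, which is a further reason to fit both terms.

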5.1 Study participant Inclusion Criteria

In order to be eligible to participate in this study, a study participant must meet all of the following criteria:

- Male or female, aged 18 to 99
- Willing to comply with all study procedures and be available for the duration of the study
- Diagnosed with IBS-C satisfying Rome IV criteria
- Have symptoms present for at least the last 3 months
- Have abdominal pain that is not adequately relieved at the time of screening and the time of randomization
- Has a VAS pain score of >3 (on 0-10 score)

5.2 Study participant Exclusion Criteria

A potential study participant who meets any of the following exclusion criteria at baseline will be excluded from participation in this study if:

- Have an unrelated active disorder which may involve abdominal pain, such as inflammatory bowel disease, diabetes, unstable thyroid disease
- Have history of abdominal surgery other than cholecystectomy (gallbladder removal) or appendectomy
- Are taking anticoagulants or antispasmodic, antidiarrheal, or opioids or other pain relief medications and cannot stop these medications for three consecutive days before each study visit
- Are pregnant or breastfeeding; women of child bearing potential complete a pregnancy test at each visit
- Have known allergic reactions to components of the ECG electrodes
- Received treatment with an investigational drug or other intervention within 6 months of the date of consent
- Anything that, in the opinion of the investigator, would place the study participant at increased risk or preclude the study participant's full compliance with or completion of the study
- Are unable to provide informed consent

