2.3 Potential Risks and Benefits

2.3.1 Potential Risks

The immediate risks involved with barostat inflation and subsequent rectal distension include:

- Discomfort during the balloon insertion
- Sensation (discomfort) with the balloon inflation which is a variable of the study. The likelihood of this risk is common, up to 100% of participants will experience discomfort. The study team will make the study participant aware of this before consenting to the procedure. The study participant has the right to stop the procedure at any time.
- Bleeding at the site of balloon inflation (in the rectum). The likelihood of this risk is rare, approximate incidence of <1%.

However, the duration of rectal distension is brief and the distension can be immediately terminated upon intolerable pain or discomfort.

The long range risk of barostat inflation is:

- Perforation of the rectum into the peritoneal space, the likelihood of this risk is rare, approximate incidence of <1%.

The risks of electrical stimulation via TEA are:

- Possible allergic reaction to the stimulation electrodes and sensation of electrical stimulation. The likelihood of this risk is rare, approximate incidence of <1%.

However, the stimulation output will be set at a level that is well tolerated by the participant. In very rare occasions, the participant might experience rash or minor infection at the stimulation point that can be treated locally if needed.

The risk involved with the ECG recording:

- Allergic reaction of ECG electrodes. The likelihood of this risk is rare, approximate incidence of <1%

The researchers will try to minimize these risks by having an experienced investigators and lab personnel performing the barostat studies with particular care. The study investigators and our GI Physiology lab staff are well versed in doing these type of procedures. In addition, one of gastroenterologist-physician study investigators will be present/perform the studies or will be readily available on site for consultation/evaluation in case of any study complications or questions.

The rationale behind these risks is that the risks are unlikely and the study participant would receive care

immediately. Moreover, the study team would not be able to collect this data without study participants enduring the risks. Alternative procedures would not provide the same understanding of the influence of TEA for IBS-C study participants.

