13.3 Informed Consent Process

Informed consent is a process that is initiated prior to the individual's agreeing to participate in the study and continues throughout the individual's study participation. Extensive discussion of risks and possible benefits of this therapy will be provided to the study participants and their families. Consent forms (written in non-technical language) describing in detail the study interventions/products, study procedures, and risks are given to the study participant and written documentation of informed consent is required prior to starting intervention/administering study product. Consent forms will be IRB-approved and the study participant will be asked to read and review the document. Upon reviewing the document, the study team member will explain the research study to the study participant and answer any questions that may arise. The study participant will sign the informed consent document prior to any procedures being done specifically for the study. The study participants should have the opportunity to discuss the study with their surrogates or think about it prior to agreeing to participate. The study participants may withdraw consent at any time throughout the course of the trial. A copy of the informed consent document will be given to the study participants for their records. The rights and welfare of the study participants will be protected by emphasizing to them that the quality of their medical care will not be adversely affected if they decline to participate in this study.

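### Users of anticoagulants, opioids and other listed medicines must start the first medication hold before they consent, with no stated physician check, and sections 4.1 and 5.2 give different hold rules

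*Combined protocol and SAP*

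**What the plan says.** **Eligibility.** Section 5.2 excludes candidates who "Are taking anticoagulants or antispasmodic, antidiarrheal, or opioids or other pain relief medications and cannot stop these medications for three consecutive days". The criterion applies to all five visits. The two conditions are joined, so taking a listed medicine does not by itself exclude anyone. A user who can stop is eligible.

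**Visit instruction.** Section 4.1 says: "48 Hours prior to the visit: The study participants will not take any medications known to affect the gut or pain perception". It names no medicines.

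**Consent.** Section 4.1 makes all visits alike, "with the exception of the first visit which will include the informed consent process". Section 7.1 agrees: "The study participant will go through the informed consent process at the first study visit". Appendix A puts consent, enema, baseline recording and a stimulation session all at visit 1. Section 13.3 says: "The study participant will sign the informed consent document prior to any procedures being done specifically for the study".

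**Medical cover.** Section 2.3.1 says that "one of gastroenterologist-physician study investigators will be present/perform the studies or will be readily available on site" for complications or questions. Section 5.2 also excludes for "Anything that, in the opinion of the investigator, would place the study participant at increased risk". Section 9.1.3 names a physician to follow serious adverse events and act as emergency contact, and notes that the principal investigator is not a physician.

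**Recording.** Appendix A has a row at each visit for laxative and antispasmodic use. It has none for anticoagulants, opioids or other pain relief. The hold is not among the risks in 2.3.1 or 10.2.1.

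**The concern.** The hold exists only because of the study. Stopping an anticoagulant or an opioid is a medical decision with possible consequences of its own, and this plan asks for it five times. As written, a person can be told at a pre-screening contact, possibly by phone and by any member of the study team, what is needed for visit 1. That person could then stop such a medicine before signing anything and before any physician has been asked whether it is safe.

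The differing hold rules matter for a second reason. Staff who worked from 4.1 alone would apply a shorter hold, and might not treat an anticoagulant as covered. The participant would then undergo rectal distension, for which 2.3.1 lists bleeding as a rare risk (below 1%).

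**Working it through.** **The plan's own figure.** Section 10.2 allows 20% dropout around 20 completers: 20 / (1 − 0.20) = 25 enrolled. This reproduces and is not in dispute. It is used below only as a count of people.

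**Inputs.** Five visits, 1 to 3 weeks apart (Protocol Summary); a three-day hold (5.2); a 48-hour hold, taken as 2 days (4.1); consent at visit 1 (4.1, 7.1, Appendix A).

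**Does the first hold precede consent?** Both rules apply before every visit, including visit 1. No separate consent visit is described. The first hold therefore starts 3 days (5.2) or 2 days (4.1) before signature. Someone on a listed medicine who waited until after signing would arrive at visit 1 without the hold, and the plan gives no route for consenting then and returning later for the session. Holds before consent: 1 of 5 = 20% under either rule. Someone already off these medicines is unaffected.

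**Hold days per affected participant who completes all visits.** Total = 5 × hold length. Span from the start of the first hold to visit 5 = hold length + 4 × gap.

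| Rule | Hold days | Weekly visits | Three-week gaps |
|---|---|---|---|
| 5.2 | 5 × 3 = 15 | 15 / (3 + 28) = 15/31 = 48% | 15 / (3 + 84) = 15/87 = 17% |
| 4.1 | 5 × 2 = 10 | 10 / (2 + 28) = 10/30 = 33% | 10 / (2 + 84) = 10/86 = 12% |

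Difference: 3 − 2 = 1 day per visit; 15 − 10 = 5 days in total. These figures describe exposure to the hold, not harm.

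**The two rules side by side.** Section 5.2 is a list: it names anticoagulants and omits laxatives. Section 4.1 is a class rule: it plausibly covers laxatives and does not name anticoagulants. They differ in length and in scope.

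**How many people?** The documents do not say. If k enrolled participants take a listed medicine up to the hold, there are k holds before consent, and 5k holds in all if each completes. Illustrations, all assumed: k = 0 gives none; k = 1 gives 1 before consent and 5 in all; k = 5 gives 5 and 25. The extreme for holds before consent is k = 25 rather than 20, because these holds occur before any dropout. It would be higher still if some candidates stopped a medicine and were then not enrolled.

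**Who decides that a medicine may be stopped?** The gastroenterologists in 2.3.1 cover the barostat sessions, and the physician in 9.1.3 covers serious adverse events. Section 9.1.1 reserves causality judgements to people qualified to diagnose, so the protocol does assign medical decisions elsewhere. No such assignment for the hold appears in the available text.

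**The case against.** **Safeguards exist.** Part of recruitment is by referral from co-investigators and physician colleagues (5.3). The investigator may exclude anyone judged at increased risk (5.2), and being unable to stop can fairly be read to include being unable to stop safely. A participant who later meets an exclusion criterion is withdrawn (5.4.2), and gastroenterologists are present or on site (2.3.1). A reader might infer that there is no medical oversight; the documents do not support that. What remains is that none of these provisions gives anyone the decision before the first hold, and candidates from the research registry (section 4) may have no referring physician.

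**The absence cannot be fully proved.** Some front pages, the phone script and the consent form are not in the available text and might deal with the hold. The statement about physician assignment is limited accordingly. The consent timing and the two hold rules are explicit in the text and do not depend on what is missing.

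**The rules can both be obeyed.** A reader might infer a direct contradiction between 4.1 and 5.2. That is too strong: for medicines under both rules, a three-day hold also satisfies 48 hours, and 5.2 can be read as an eligibility test with 4.1 as the visit instruction. Continued anticoagulant use up to distension would require 4.1 to be followed without 5.2, and nothing says that it would be. The inconsistency still stands, because 5.2 also applies before each visit and a site has no single rule to follow.

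**A hold may not be a procedure.** A reader might infer an outright breach of 13.3. That section speaks of procedures, and withholding one's own medicine is arguably not one. Section 7.1 also has the study explained before visit 1. An explanation is not signed consent, however, so the departure is from the intent of 13.3 rather than plainly from its letter.

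**Conclusion.** The point holds as a gap in consent timing and safety that is cheap to close. A current user of a medicine listed in 5.2 who follows the plan begins one of five holds before consent. In the available text, no physician is assigned to judge whether an anticoagulant or opioid may safely be stopped. Sections 4.1 and 5.2 are inconsistent by 1 day per visit (5 in total) and in which medicines they cover.

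This rests on consent taking place at visit 1 as 4.1, 7.1 and Appendix A state, and on at least one candidate taking a listed medicine until the hold. The number affected may be zero, and every participant count above is assumed. The documents give no rate of harm from stopping, so none is claimed. Sample size and analysis are untouched. Reporting is not the issue either: adverse events on study are recorded whatever their cause (9.1.1) and reported to the IRB (9.2.2).

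**What to change.** 1. **Consent and medical check.** For candidates taking a medicine listed in 5.2, obtain consent before the first hold. Have a physician already on the study document that the medicine may safely be stopped for the visits; otherwise exclude.
2. **One rule.** State a single hold length and a single medicine list in both 4.1 and 5.2, and check that list at each visit in Appendix A. Length and list are for the clinicians to set; none is proposed here.

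As accompanying wording, list the hold among the risks in 2.3.1 and 10.2.1.

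**Cost.** Amended text in these places, an earlier consent contact and a documented sign-off for the candidates concerned. Visit 1 may be later for them, and some may be excluded; the documents do not allow a count. If the merged list takes in laxatives, applying the sign-off to everyone on it could be burdensome in a constipation population. In that case, limit it to anticoagulants, opioids and any other medicine the clinicians consider risky to stop.
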